## Appendix 1 Schedule of Activities (cont.)

maintained for each ECG evaluation to prevent changes in heart rate. Environmental distractions (e.g., television, radio, conversation) should be avoided during the pre-ECG resting period and during ECG recording. ECGs for each patient should be obtained from the same machine whenever possible.

- o Triplicate digital ECG recordings are required pre-dose (Day 1) and 2 hours  $\pm$  30 minutes post dose for Week 24 only. The ECG intervals (e.g., PR, QRS, QT, QTcF, and RR) and heart rate from these three ECGs will be entered into the eCRF, in addition, these triplicate readings will be stored for future analysis, if needed
- p Not required if documented results are available of a chest radiograph (read by a radiologist) taken within the 12 weeks preceding the screening visit.
- q PPD should be performed only if QFT (which is to be used as the initial TB screening test) is not available. For the Week 44 visit, follow the same method of testing and assessment that was completed during screening period.
- r *Can be collected as needed to complete SLEDAI-2K or BILAG-2004 assessments, e.g. myositis.*
- s Includes HBsAg, HBsAb, HBeAb, HCV Ab.
- t The Coombs test *should* be performed at a local laboratory.
- u Includes hemoglobin, hematocrit, RBC count, calculated indices (MCV, MCH, MCHC, RDW), platelet count, and WBC count with differential.
- v Includes electrolytes (Na, K, Cl, bicarbonate, phosphorus), urea, creatinine, glucose, ALT, AST, amylase, lipase, total and direct bilirubin, alkaline phosphatase, GGT, albumin, globulin, total protein, calcium, uric acid
- w Includes INR, aPTT, and PT.
- x Includes total immunoglobulins, IgG, IgM, IgE, and IgA.
- y All women of childbearing potential (including those who have had a tubal ligation) will have a serum pregnancy test at screening. Urine pregnancy tests will be performed locally at specified subsequent visits. If a urine pregnancy test is positive, it must be confirmed by a serum pregnancy test (performed locally).
- z Once treatment with study medication begins, TBNK results will be blinded.
- aa Includes dipstick (blood, protein, glucose, nitrites, and leukocyte esterase), microscopic analysis (RBC, WBC, red cell casts, white cell casts).
- bb C3, C4, and CH50 conducted monthly on the same day as the SLEDAI-2K.
- cc Autoantibody panel includes anti-Smith, anti-RNP, anti-Ro, anti-La, anti-cardiolipin, and anti-beta 2 glycoprotein
- dd A FMV urine sample must be collected at Weeks 0, 4, 24, and 48. FMV urine samples should be collected at all other indicated visits unless the patient forgets to collect the FMV or forgets to bring the urine to the visit (refer to laboratory manual for details on urine collection instructions), in which case a random urine sample is acceptable.
- ee Screening urine sample needs to be a FMV (in mg/mg) and must be collected during the screening period (refer to laboratory manual for details on urine collection instructions). Patients will receive the urine collection kit at the first screening visit and will bring the FMV urine collection to the second screening visit.

## Appendix 1 Schedule of Activities (cont.)

- ff Collect prior to drug administration.
- gg Collect PK samples at four timepoints: prior to study drug, 2 hours ( $\pm$  30 minutes) post-dose (fasting), 4–6 hours post-dose, and 8–10 hours post dose (U.S. sites only). If the patient is unable to stay or return to clinic for the post-dose 8-10 hour timepoint, this sample may be collected by a home nurse visit.
- hh Sample to be collected at baseline. However, if sample not drawn at baseline, it may be collected at any other timepoint.
- ii Three PaxGene whole blood tubes to be collected prior to study drug administration for PD sample. Please see laboratory manual for PaxGene blood sample handling.
- jj Collect serum and plasma tubes prior to study drug administration for PD biomarker serum and PD biomarker plasma.
- kk *U.S. sites only*: Blood for PBMCs will be shipped overnight to a central laboratory for processing. To be performed at centers where samples can be shipped to central laboratory within 24 hours.
- ll *U.S. and selected sites only*: Includes multi-color flow cytometry analysis of B cells and B cell subsets
- mmm Includes multi-color flow cytometry analysis of basophil activation. To be performed at centers in the United States where samples can be shipped to FACS laboratory within 24 hours.
- nn *U.S. sites only*: Blood for PBMCs will be shipped overnight to a central laboratory for processing and cryopreserved. To be performed at centers where samples can be shipped to central laboratory within 24 hours.
- oo Fasting lipid panel includes triglycerides, HDL, LDL, HbA1c, and total cholesterol. The patient should be fasting ( $\geq$  4 hours).
- pp For patients with arthritis present at current visit prior to Week 24 or any past visit during the study.
- qq WGS and photography are contingent upon the review and approval by each site's IRB/EC and, if applicable, an appropriate regulatory body.
- rr The same clinician *is strongly recommended to* complete the Physician's Global Assessment throughout the study.
- ss To ensure instrument validity and that data standards meet health authority requirements, the questionnaire will be self-administered before the patient or clinician receives any information on disease status, prior to the performance of non-PRO assessments, and prior to the administration of study treatment, unless otherwise specified. See [Appendix 17](#) for sample questionnaires for FACIT-Fatigue.
- tt Patients will receive GDC-0853/placebo BID starting on Day 1 and ending on the evening (p.m. dose) prior to the Week 48 visit. GDC-0853/placebo should be taken with water by mouth. The dates and times of the most recent prior meal and most recent prior dose of short-acting antacid, PPI, or H2RA, last dose of oral study drug (prior to clinic visit), and timing of study drug administration in clinic (if applicable) should be recorded at each clinic visit.
- uu Not applicable for a site that has not been granted approval for RBR sampling.

## Appendix 2

### Schedule of Pharmacokinetic and Biomarker Samples

Visit	Timepoint	Sample Type	
Screening (Day -35 to Day -1)	NA	Blood for PD RNA PD biomarker serum PD biomarker plasma Blood for PBMC ( U.S. Sites only ) Flow cytometry (B-cell subsets) ( U.S. and selected sites only ) Flow cytometry (basophils) ( U.S. sites only ) Blood for serum for RBR (optional) Blood for RNA for RBR (optional)	
Day 1 a , 29, 337 (Weeks 4 and 48)	Prior to dose (to be administered in clinic if applicable)	Blood for PK Blood for PG ( Day 1 only ) Blood for PD RNA PD biomarker (serum) PD biomarker (plasma) Exploratory urinary biomarker collection (first void) Blood for PBMC ( U.S. sites only ) Flow cytometry (B-cell subsets) ( U.S. and selected sites only ) Flow cytometry (basophils) ( U.S. sites only ) ( Days 1 and 29 only ) Blood for immunophenotyping ( U.S. sites only ) ( Day 1 only ) Blood for serum for RBR (optional) ( Days 1 & 337 only ) Blood for RNA for RBR (optional) ( Days 1 & 337 only ) Blood for WGS for RBR (optional) ( Day 1 only )	
Day 85 (Week 12)	Prior to dose	Blood for serum for RBR (optional) Blood for RNA for RBR (optional)	
Day 169 a (Week 24)	Prior to dose (must be administered in clinic if applicable)	Blood for PK Blood for PD RNA PD biomarker (serum) PD biomarker (plasma) Exploratory urinary biomarker collection (first void) Blood for PBMC ( U.S. sites only ) Flow cytometry (B-cell subsets) ( U.S. and selected sites only ) Flow cytometry (basophils) ( U.S. sites only ) Blood for immunophenotyping ( U.S. sites only ) Blood for serum for RBR (optional) Blood for RNA for RBR (optional)	
		2 hr ( $\pm$ 30 min) post dose, fasting	Blood for PK
		4–6 hr post dose	Blood for PK

## Appendix 2 Schedule of Pharmacokinetic and Biomarker Samples (cont.)

Visit	Timepoint	Sample Type
	8–10 hr post dose (U.S. sites only) b	Blood for PK
Day 393 (SFU) (Week 56)	Prior to dose	Blood for PD RNA PD Biomarker (serum) PD biomarker (plasma) Exploratory urinary biomarker collection (first void) Blood for PBMC ( U.S. sites only ) Flow cytometry (B-cell subsets) ( U.S. and selected sites only )
UV, FV or ET visits	NA	Blood for PK Blood for PD RNA ( FV and ET only ) PD biomarker (serum) ( FV and ET only ) PD biomarker (plasma) ( FV and ET only ) Exploratory urinary biomarker collection (first void) ( FV and ET only ) Blood for PBMC ( U.S. sites only ) ( FV and ET only ) Flow cytometry (B-cell subsets) ( U.S. and selected sites only ) ( FV only ) Flow cytometry (basophils) ( U.S. sites only ) ( ET only ) Blood for serum for RBR (optional) ( FV only ) Blood for RNA for RBR (optional) ( FV only )

ET=early termination visit; FACS= fluorescence-activated cell sorting; FV=flare visit; H2RA=H2 receptor antagonist; hr=hours; min=minutes; NA=not applicable; PBMC= peripheral blood mononuclear cell; PD=pharmacodynamics; PG =pharmacogenomics; PK=pharmacokinetic; PPI=proton-pump inhibitor; RBR=Research Biosample Repository; SFU= Safety Follow Up Visit; U.S.=United States; UV=unscheduled visit.

Note: Study assessments may be delayed or moved ahead of the window to accommodate holidays, vacations, and unforeseen

Morning clinic visits are preferred for all visits but are especially encouraged on Day 1 and Week 24. Prior to visits on Day 1, Week 4, and Week 24, patients should be instructed not to take their morning dose and to bring their study medication with them to their clinic visit. For all visits with PK samples, the date and time of the last dose of study drug, last dose of acid-reducing medication (PPI, H2RA, or short-acting antacid), and last meal should be recorded, along with the actual time of the PK blood draw. The procedures for collection, handling, and shipping of PK samples can be found in the study's Laboratory Manual.

a Morning visit is strongly recommended. Patients must be fasting ( $\geq 4$  hours) prior to the pre-dose PK draw.

b **U.S. sites only:** If the patient is unable to stay or return to clinic for the post-dose 8–10 hour timepoint, this sample may be collected by a home nurse visit on the Week 24 visit.

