### **3.3.5 Rationale for PK Sample Collection Schedule**

PK results will be used to perform robust exposure-response and exposure-safety analyses, which will help to characterize how safety and efficacy are impacted by drug exposure and, thus, inform appropriate doses and regimens for future studies of GDC-0853. The PK sampling schedule is designed to capture data at several points during the study in order to *enable the estimation of systemic GDC-0853 exposures and subsequent* exposure-response evaluations and dose-regimen selection for future studies (see [Appendix 2](#)), *which may be reported separately*.

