#### **4.3.1 Formulation, Packaging, and Handling**

##### **4.3.1.1 GDC-0853 50-mg Tablet and Placebo Tablet**

GDC-0853 will be provided by the Sponsor as 50-mg dose strength tablets with corresponding matching placebo tablets, which will be indistinguishable in appearance. Tablets will be supplied in blister wallets for the treatment arm to which the patient is randomized. GDC-0853 and placebo tablets should be stored at 2°C–8°C.

For information on the formulation and handling of GDC-0853, see the GDC-0853 Investigator's Brochure.

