#### **4.3.2 Dosage, Administration, and Compliance**

##### **4.3.2.1 GDC-0853 and Placebo Dose and Administration**

The GDC-0853 dose levels are 150 mg QD and 200 mg BID with matching placebo (see [Table 2](#)). Patients will receive GDC-0853/placebo BID approximately every 12 hours starting on Day 1 and ending on the evening (p.m. dose) prior to the Week 48 visit. Patients should be directed to take one dose (a total of 4 tablets) BID (total of 8 tablets each day). On clinic visit days when PK assessments are performed (Day 1, Week 4, and Week 24), patients should be instructed that study drug will be administered in the clinic.

In general, a dosing window of  $\pm 2$  hours is acceptable. If a dose is taken more than 2 hours late or is missed altogether, the patient should resume normal dosing with the

next scheduled dose. Patients should record the dose that was missed on the blister wallet. Doses that are vomited will be considered missed doses.

GDC-0853 or placebo will be orally administered and may be taken with or without food, except the dose of oral study drug taken at the clinic visit on Day 1 and Week 24 (see Section 4.4.4 and Appendix 1 and Appendix 2), which will be administered at the clinic visit while fasting. The dates and times of the most recent prior meal, last dose of oral study drug (prior to clinic visit), and timing of oral study drug administration in clinic should be recorded at clinic visits with PK and/or fasting lipid assessments. In addition, any use of PPIs, H2 receptor antagonists (H2RAs), and/or short-acting antacids (e.g., Maalox®, Pepto-Bismol®, Roloids®) should be recorded as concomitant medications, including date and time of last administration prior to the PK clinic visits. Administration of study drug should be staggered with short-acting antacid use (i.e., oral study drug should be taken 2 hours before or 2 hours after the short-acting antacid). Staggering is not required for PPIs or H2RAs; however, PPI and H2RA medications *are recommended* to be maintained at a constant dose and regimen throughout the study if possible.

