**Table 2 Study Drug Dosing Regimen by Treatment Arm**

Arm	GDC-0853 Dose (mg)	Number of GDC-0853 Tablets (a.m./p.m.)	Number of placebo (a.m./p.m.)
A	200 BID	4/4	0/0
B	150 QD	3/0	1/4
C	0	0/0	4/4

a.m. = in the morning; BID = twice daily; p.m. = in the afternoon; QD = daily.

Note: All patients will take 4 tablets BID (i.e., 8 tablets daily) regardless of assigned GDC-0853 dose regimen in order to maintain the blind.

At study visits, sufficient study medication will be dispensed to complete dosing until the next scheduled visit. When study medication is administered at the site, it will be administered under supervision of study personnel, and the amount of study medication dispensed must be recorded.

Any overdose or incorrect administration of study drug should be noted on the Study Drug Administration electronic Case Report Form (eCRF). Adverse events associated with an overdose or incorrect administration of study drug should be recorded on the Adverse Event eCRF.

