#### **4.3.2.2 GDC-0853 and Placebo Compliance**

The following measures will be taken to assess patient compliance with study drug: Sites will be responsible for prepopulating the dates on the blister wallets for when patients are scheduled to take study drug. Under the corresponding dates listed, the patients will record the times (a.m. or p.m.) that they take each dose directly on the blister wallet. Patients should only remove tablets from the wallet at the time they take

the tablets (e.g., patients should not transfer the tablets to another container with their other medications for future use). Patients will be instructed *by the site staff on how to properly take the study drug, including recording the IP intake time on the blister wallet and a reminder to bring all blister wallets (used and unused) to each study visit for assessment of compliance (based on the tablets remaining in the wallets as well as the recorded dates and times) and for medication disposal.*

Compliance will be documented on the source record. If compliance is  $\leq 80\%$  (correct dosage at the correct time), the investigator or designee is to counsel the patient and ensure steps are taken to improve compliance.

*In order to maintain the proper source documentation of subjects' IP compliance, the investigator should follow one of the two processes listed below:*

- 1. The site will keep the blister wallets on-site, together with all other subject source documents (e.g. signed ICFs, medical notes, completed PROs, etc.). Blister wallets may not be destroyed until all trial related documents are approved to be discarded if this process is followed.*
- 2. Site staff will generate certified copies of the blister wallets, showing IP intake times recorded by the subjects on the wallets. After PI accountability is performed, blister packs are checked by the site monitor, and sponsor approval is obtained, the blister packs may be destroyed at the site or returned for destruction. If the investigator chooses to follow this process, all copies of blister wallets must be signed and dated by the person making the copy and noted with a statement such as "I certify that this is the true and correct copy of the original." For this trial, only printed copies of blister wallets will be accepted. Electronic copies are not allowed.*

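### In Arm B the dose time recorded for the Week 4, 24 and 48 pre-dose PK samples is that of an all-placebo evening dose, and the plan does not link the active morning dose time to the PK data

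*Combined protocol and SAP*

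**What the plan says.** **Regimen.** Under Table 2, Arm B takes 3 active and 1 placebo tablet in the morning, and 0 active and 4 placebo tablets in the evening. Arm A takes 4 active tablets each time. The tablet count is the same in every arm: "All patients will take 4 tablets BID (i.e., 8 tablets daily) regardless of assigned GDC-0853 dose regimen".

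**Timing of the draws.** Before the Day 1, Week 4 and Week 24 visits, "patients should be instructed not to take their morning dose and to bring their study medication with them to their clinic visit" (Appendix 2). Section 4.3.2.1 and Appendix 1 footnote c end dosing on the evening before Week 48.

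**What is recorded at a PK visit.** Appendix 2 requires "For all visits with PK samples, the date and time of the last dose of study drug", together with acid-reducing medication, last meal and actual draw time. Section 4.3.2.1 and Appendix 1 footnote tt likewise ask for the "last dose of oral study drug (prior to clinic visit") and for the time of the dose given in clinic. None of the three asks for more than one dose before the visit.

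**What is recorded elsewhere.** Under Section 4.3.2.2, "the patients will record the times (a.m. or p.m.) that they take each dose directly on the blister wallet". Missed doses are marked there too (Section 4.3.2.1). The wallets come to every visit for the compliance check and are kept on site, or as certified paper copies.

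**Intended use.** Section 3.3.5: "PK results will be used to perform robust exposure-response and exposure-safety analyses". These are to inform doses and regimens for later studies. Section 6.6 tabulates and summarizes concentrations by visit, says inter-patient variability will be evaluated, and leaves exposure-response exploration optional.

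**The concern.** A trough sample can be used for exposure estimation only if the time since the last active dose is known. The identical tablet count protects the blind, but it also means that the most recent study-drug dose is not always the most recent active dose. In Arm A the recorded evening dose is active, so the field is right. In Arm B it is placebo, so the field describes the wrong dose. The problem is confined to one of the two active arms, and it affects data meant to support exposure-response analysis and dose selection across both. Blinded site staff cannot correct it on their own initiative, because they do not know for which patients the previous morning's dose is the one that matters.

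**Working it through.** **1. Reproduce the regimen.** Section 4.3.1.1: "GDC-0853 will be provided by the Sponsor as 50-mg dose strength tablets".
- Arm B morning: 3 × 50 = 150 mg. Evening: 0 × 50 = 0 mg. Tablets: 3 + 1 = 4 and 0 + 4 = 4.
- Arm A: 4 × 50 = 200 mg at each dose.

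This agrees with the stated 150 mg QD and 200 mg BID.

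**2. Identify the last dose before each scheduled pre-dose sample.**

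| Sample | Last study-drug dose | Arm A | Arm B |
|---|---|---|---|
| Day 1 | none | – | – |
| Week 4 | previous evening | active | placebo |
| Week 24, pre-dose | previous evening | active | placebo |
| Week 48 | previous evening | active | placebo |

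The Week 24 post-dose samples are timed from the clinic dose, which is active in Arm B and is recorded.

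**3. Time intervals in Arm B.** Section 4.3.2.1 gives doses about 12 h apart with a ±2 h window. Put the previous morning's dose at 0 h (±2), the evening dose at 12 h (±2) and the draw at 24 h.
- Since the recorded (placebo) dose: 24 − 12 = 12 h, range 10 to 14 h.
- Since the last active dose: 24 − 0 = 24 h, range 22 to 26 h.

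A draw later than usual widens both ranges. Its clock time is known, but the start of the active interval is not in the PK record.

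**4. Number of samples.** 240 patients randomized 1:1:1 gives about 80 in Arm B, and 80 × 3 = 240 samples at most. That is 3 of 5 scheduled post-baseline samples per patient, or 3 of 6 at U.S. sites, which add the 8–10 h draw.

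**5. Size of the error.** The documents give no half-life. Assume mono-exponential decline with a half-life h of 4 to 12 h. An error of d hours in time since dose misstates the expected concentration by 2^(d/h).

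| h (assumed) | d = 2 h: nominal 24 h used, dose at edge of window | d = 12 h: placebo time taken as active | d = 24 h: one missed a.m. dose, unnoticed |
|---|---|---|---|
| 4 h | 1.41 | 8 | 64 |
| 8 h | 1.19 | 2.8 | 8 |
| 12 h | 1.12 | 2 | 4 |

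The first column is the ordinary case. The other two need an extra failure, discussed under the objection.

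**The case against.** A reader might infer that the time since active dose is not captured at all. The documents do not support that. Section 4.3.2.2 puts the time of every dose on a dated wallet that is checked at each visit and retained as source. What is missing is transcription and linkage.

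A reader might also take the 2- to 8-fold column as the expected error. It requires an analyst to treat a known placebo dose as active. Section 4.2 leaves the staff doing PK/PD assessments unblinded, and Table 2 shows which dose is active, so a nominal 24 h is the likelier choice. The 4- to 64-fold column requires a missed morning dose that neither the patient's wallet entry nor the tablet check brings to the analyst's notice. Incorrect administration also goes on the Study Drug Administration eCRF, although the protocol does not say whether a missed dose counts as such.

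Other limits are fair. Day 1 precedes all dosing. At unscheduled, flare or early-termination visits the last dose may be the active one. Section 6.6 plans summaries by visit that do not use time since dose, and exposure-response work may be reported separately. The eCRF pages and Laboratory Manual are not among the documents, so an a.m. dose field may exist there.

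These points narrow the concern but do not remove it. The wallet is described as a compliance record, electronic copies are not allowed, and no section sends its times to the PK dataset. As the protocol is written, an analyst who wanted the morning times would have to retrieve paper from the sites. A nominal 24 h neither reflects real dosing times nor shows a missed dose.

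**Conclusion.** The point holds as a gap in the PK-visit record, not as a loss of the data. For the Week 4, 24 and 48 pre-dose samples in Arm B, up to about 240 samples in about 80 patients, the dose time that the protocol requires belongs to a placebo dose. The active dose time stays in site source documents with no stated route to the PK data.

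If a nominal 24 h is used, a 2 h difference in the morning dose costs about 1.12- to 1.41-fold in expected concentration. This rests on mono-exponential decline and an assumed half-life of 12 to 4 h. The error is larger where a missed morning dose is not picked up from the wallet. The by-visit summaries are little affected, apart from some added apparent variability. The exposure-response and exposure-safety work has more to lose, because the error falls on one dose arm only. The efficacy analyses are not touched. This is a cheap improvement worth making, not a flaw that undermines the trial.

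**What to change.** In Section 4.3.2.1, Appendix 1 footnote tt and Appendix 2, replace the single last-dose item. At each PK visit, for every arm, record the date and time of both the last a.m. and the last p.m. dose before the draw, and whether each was taken in full. State that these are transcribed from the blister wallet to the eCRF and linked to the PK sample. Asking for both in all arms keeps the blind, and the unblinded PK analyst then selects the active dose from Table 2.

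The cost is one or two extra eCRF fields per PK visit, copied from a wallet that the patient already brings and the site already checks. No sample, visit or unblinding is added.
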